Appendix C

Small Intestinal Bacterial Overgrowth (SIBO) Protocol

Dietary Recommendations

Follow the low FODMAP diet at the guidance of a healthcare professional. See included Stanford University Medical Center FODMAP handout for a brief introduction to this diet.

Duration

This protocol is designed to take 8 weeks.

Product Overview

Category	Products	Servings per Bottle	Capsules per Day	Duration	Number of Bottles*
Detox Support	Liver-G.I. Detox	60 capsules	2 per day	30 days	One bottle
GI Support	L-Glutamine Powder	73 scoops	2 scoops per day	35 days	One bottle
Microbial Balance	MicroDefense	90 capsules	1 per day	49 days	One bottle
Microbial Balance	A.C. Formula II	120 capsules	4 per day	49 days	Two bottles
Probiotic	Probiotic-5	60 capsules	1 per day	49 days	One Bottle
Digestive Enzymes	Digestive Enzymes Ultra with Betaine HCl**	180 capsules	As needed (up to 6)	Long term	One bottle

*The number of capsules purchased may exceed the amount required by this protocol, due to limited bottle sizes.

**Digestive Enzymes Ultra with Betaine HCl may be replaced with Digestive Enzymes Ultra, if patient responds poorly to Betaine HCl.

Protocol

	Product	Breakfast	Lunch	Dinner
Week 1	Liver-G.I. Detox	1 capsule		1 capsule
	Digestive Enzymes Ultra with Betaine	1-2 capsules or as needed before meal	1-2 capsules or as needed before meal	1-2 capsules or as needed before meal
Weeks 2 – 5	Liver-G.I. Detox (finish 2 days into week 5)	1 capsule		1 capsule
	Digestive Enzymes Ultra with Betaine	1-2 capsules or as needed before meal	1-2 capsules or as needed before meal	1-2 capsules or as needed before meal
	L-Glutamine	1 serving	1 serving	
	A.C. Formula II	2 capsules before meal	2 capsules before meal	
	MicroDefense		1 capsule before meal	
	Probiotic-5			1 capsule
Week 6	Digestive Enzymes Ultra with Betaine	1-2 capsules or as needed before meal	1-2 capsules or as needed before meal	1-2 capsules or as needed before meal
	L-Glutamine	1 serving	1 serving	
	A.C. Formula II	2 capsules before meal	2 capsules before meal	
	MicroDefense		1 capsule before meal	
	Probiotic-5			1 capsule
Weeks 7 & 8	Digestive Enzymes Ultra with Betaine	1-2 capsules or as needed before meal	1-2 capsules or as needed before meal	1-2 capsules or as needed before meal
	A.C. Formula II	2 capsules before meal	2 capsules before meal	
	MicroDefense		1 capsule before meal	
	Probiotic-5			1 capsule

Low-FODMAP Food Plan

PROTEINS

Proteins

Lean, free-range, grass-fed, organically grown animal protein; non-GMO, organic plant protein; and wild-caught, low-mercury fish preferred. Canned meats are allowed if cans are BPA-free and if the meat is free of high-FODMAP fillers.

Animal Protein:

- Cheese (hard): cheddar, colby, feta, havarti, manchego, Pecorino, Swiss— $\frac{1}{2}$ oz
- Cheese (soft): brie, Camambert, chevre, goat cheese, mozzarella—1 oz
- Cottage cheese (dry curd)— $\frac{1}{4}$ c
- Cream cheese—2 T
- Parmesan cheese—2 T
- Ricotta cheese—2 T
- Egg—1, or 2 egg whites
- Fish/shellfish: Anchovies, clams, cod, flounder, halibut, salmon, sardines, trout, tuna, etc.—1 oz
- Meat: beef, buffalo, elk, lamb, pork, venison, other wild game—1 oz
- Poultry (skinless): Chicken, Cornish hen, duck, pheasant, turkey, etc.—1 oz

Plant Protein:

- Spirulina—2 T
- Tempeh—1 oz
- Tofu (firm/extra firm)— $1\frac{1}{2}$ -2 oz

Protein Powder:

- Check label for # grams/scoop (1 protein serving=7 g)
- Bovine collagen, egg, hemp, whey protein isolate

1 serving as listed = 35-75 calories, 5-7 g protein, 3-5 g fat, 0-4 g carbs

Average protein serving is 3-4 oz (size of palm of hand).

LEGUMES

Proteins/Carbs

Organic, non-GMO preferred

- Black beans (canned only)— $\frac{1}{4}$ c
- Green peas (cooked)— $\frac{1}{8}$ c
- Chickpeas (canned only)— $\frac{1}{4}$ c
- Hummus—1 T
- Mung beans (cooked)— $\frac{1}{4}$ c

1 serving = 90-110 calories, 3-7 g protein, 0 fat, 15 g carbs

DAIRY & ALTERNATIVES

Proteins/Carbs

Unsweetened, organic preferred

Dairy:

- Milk (plain): Lactose-free cow, goat—8 oz
- Yogurt (plain): Lactose-free cow, goat—4-6 oz

Dairy Alternatives:

- Milk: Almond, hemp—8 oz
- Milk: Coconut—4 oz
- Milk: Rice—6 oz
- Yogurt (plain): coconut—4-6 oz

1 dairy serving = 90-150 calories, 7-8 g protein, 12 g carbs

1 dairy alternative serving = 25-90 calories, 1-9 g protein, 1-4 g carbs (nutritional values vary)

Eliminate

Buttermilk, evaporated milk, goat milk, heavy cream, kefir, oat milk, sour cream, soy milk, sweetened condensed milk, yogurt (except those listed), and any other lactose-containing dairy products. Check milk substitutes for high-FODMAP sweeteners and additives. Unsweetened homemade dairy alternatives are preferred.

NUTS & SEEDS

Proteins/Fats

Unsweetened, unsalted, organic preferred

- Almonds—6
- Brazil nuts—2
- Chia seeds—1 T
- Chestnuts—5
- Coconut (fresh)— $\frac{1}{3}$ c
- Coconut (dried, shredded)—3 T
- Flax seeds— $\frac{1}{2}$ T
- Hazelnuts—5
- Macadamias—2-3
- Nut and seed butters: Almond, tahini (sesame seed)— $\frac{1}{2}$ T
- Nut flour/meal: Almond— $\frac{1}{4}$ c
- Peanuts—10
- Pecan halves—4
- Pine nuts—1 T
- Pumpkin seeds—1 T
- Sesame seeds—1 T
- Sunflower seeds— $\frac{1}{2}$ T
- Walnut halves—4

1 serving = 45 calories, 5 g fat

Eliminate

Cashews and pistachios.

FATS & OILS

Fats

Minimally refined, cold pressed, organic, non-GMO preferred

- Avocado—2 T or $\frac{1}{8}$ whole
- Butter/ghee (clarified butter, grass-fed)—1 t
- Coconut milk, regular (canned)—1 $\frac{1}{2}$ T
- Coconut milk, light (canned)—3 T
- Mayonnaise (unsweetened)—1 t
- Oils, cooking: Avocado, coconut, ghee, olive (extra virgin), rice bran, sesame—1 t
- Oils, salad: Almond, avocado, flaxseed oil, hempseed, olive (extra virgin), safflower (high-oleic), sesame, sunflower (high-oleic), walnut—1 t
- Olives: Black, green, Kalamata—8
- Pesto (olive oil)—1 t

1 serving = 45 calories, 5 g fat

Eliminate

Chocolate, soybean oil, and any salad dressings or sauces made with sweeteners or other high-FODMAP additives.

Items in orange indicate moderate- and high-FODMAP foods that may be tolerated in reduced serving sizes, as specified. Limit orange foods to a maximum 1 serving from each food category daily.

Notes: Nutritional amounts are based on average values for the variety of foods within each food category.

Dietary prescription is subject to the discretion of the health practitioner.

VEGETABLES Non-starchy

Carbs

- Artichoke hearts** (canned)— $\frac{1}{8}$ c
- Arugula
- Asparagus**—1 spear
- Bamboo shoots
- Beets** (cubed)— $\frac{1}{4}$ c
- Bok choy
- Broccoli**— $\frac{1}{4}$ c
- Cabbage: Green, purple, **Savoy**
- Carrots
- Celeric root
- Celery**— $\frac{1}{4}$ med stalk
- Chard/Swiss chard
- Chervil
- Chives
- Cilantro
- Cucumbers
- Daikon radishes
- Eggplant
- Endive
- Escarole
- Fennel
- Fermented vegetables: **Kimchi, sauerkraut**—1 T
- Green beans
- Greens: Beet, collard, kale, mustard, turnip, etc.
- Ginger root—1 t
- Horseradish
- Kohlrabi
- Lettuce, all
- Microgreens
- Parsley
- Parsnips
- Peppers, all
- Pumpkin** (canned only)— $\frac{1}{4}$ c
- Radicchio
- Radishes
- Scallions (green part only)—2 T
- Sea vegetables
- Snow peas**—5 pods
- Spinach
- Sprouts: Alfalfa, bean
- Squash: Delicata, chayote, spaghetti, yellow, zucchini
- Tomato
- Tomato juice— $\frac{3}{4}$ c
- Tomato paste, sauce (unsweetened)
- Turnips
- Vegetable juice— $\frac{3}{4}$ c
- Water chestnuts
- Watercress

1 serving = $\frac{1}{2}$ c, 1 c raw greens = 25 calories, 5 g carbs

Eliminate

Bittermelon, Brussels sprouts, cauliflower, dandelion greens, garlic, jicama, leeks, mushrooms, okra, onion, shallots, sugar snap peas, sunchoke (Jerusalem artichokes), and sweet corn.

VEGETABLES Starchy

Carbs

- Acorn squash (cubed)—1 c
- Butternut squash** (cubed)— $\frac{1}{4}$ c
- Plantain— $\frac{1}{3}$ c or $\frac{1}{2}$ whole
- Potato: Purple, red, sweet, yellow— $\frac{1}{2}$ med
- Potatoes (mashed)— $\frac{1}{2}$ c
- Root vegetables: Parsnip, rutabaga, taro, turnip— $\frac{1}{2}$ c
- Yam— $\frac{1}{2}$ med

1 serving = 80 calories, 15 g carbs

Organic, non-GMO fruits, vegetables, herbs and spices preferred

FRUITS

Carbs

Unsweetened, no sugar added

- Banana— $\frac{1}{2}$ med
- Blueberries— $\frac{3}{4}$ c
- Cranberries— $\frac{3}{4}$ c
- Dried fruit: Cranberries, currants, Gogi berries, papaya, pineapple, raisins**—1 T
- Grapefruit**— $\frac{1}{2}$ med
- Grapes—15
- Guava—1 med
- Kiwi—1 med
- Melon, all—1 c
- Orange—1 sm
- Papaya—1 c
- Passionfruit—1 med
- Pineapple— $\frac{3}{4}$ c
- Pomegranate seeds**— $\frac{1}{4}$ c
- Raspberries—1 c
- Rhubarb—1 c
- Starfruit—1 med
- Strawberries— $\frac{1}{4}$ c
- Tangerines—2 sm

1 serving = 60 calories, 15 g carbs

Eliminate

Apples, applesauce, apricots, blackberries, boysenberries, cherries, dates, figs, lychee, mango, nectarines, peaches, pears, persimmon, plums, prunes, watermelon, and all canned fruit.

WHOLE GRAINS (100%)

Carbs

Unsweetened, organic preferred

Gluten Free:

- Amaranth**— $\frac{1}{4}$ c
- Buckwheat— $\frac{1}{2}$ c
- Cereal: Corn, quinoa**— $\frac{1}{2}$ c
- Cous cous: Corn, rice**— $\frac{1}{4}$ c
- Flours: Buckwheat, corn, cornstarch, millet, quinoa, rice, teff, potato, tapioca
- Grits: corn (polenta)— $\frac{1}{2}$ c
- Millet— $\frac{1}{2}$ c
- Oats: quick (rolled)**— $\frac{1}{4}$ c
- Oats: steel-cut— $\frac{1}{2}$ c
- Quinoa— $\frac{1}{2}$ c
- Popcorn—1 c
- Rice: Basmati, black, brown, purple, red, white, wild— $\frac{1}{3}$ c
- Sorghum— $\frac{1}{8}$ c
- Teff— $\frac{3}{4}$ c

Gluten Containing:

- Bulgur**— $\frac{1}{4}$ c
- Spelt**— $\frac{1}{4}$ c

Individual portions:

- Bread—1 slice
- Pasta— $\frac{1}{3}$ c
- Tortilla—1, 6 in

All grain servings are for cooked amounts.

1 serving = 75–110 calories, 15 g carbs

Eliminate

Eliminate any breads, cereals, crackers, pastas, etc., made from wheat, rye, and barley. This includes cous cous (wheat), flour tortillas, freekeh, granola mixes, naan, Roti, sprouted bread.

BEVERAGES, SPICES & CONDIMENTS

- Filtered water
- Sparkling/mineral water
- Coconut water**—4 oz
- Coffee
- Fruit juice: Orange, cranberry**—4 oz
- Tea: Black, chai green, peppermint, white
- Tea (diluted): Chamomile, herbal, oolong**
- Cacao powder
- Cocoa powder
- Herbs: basil, cilantro, curry leaves, kafir lime, lemongrass, mint, parsley, rosemary, sage, tarragon, thyme, watercress
- Spices, all
- Condiments: Fish sauce, ketchup (unsweetened), lemon/lime juice, miso paste, mustard, vinegar (apple cider, **balsamic**, rice wine), Worcestershire sauce—use sparingly, suggest 1 T or less per serving

Approved sweeteners: Maple syrup, molasses, Stevia—use sparingly, suggest 1 t.

Eliminate

Artificial sweeteners, dandelion tea, fruit juice (except those listed), garlic salt, honey, and onion salt.

Items in orange indicate moderate- and high-FODMAP foods that may be tolerated in reduced serving sizes, as specified. Limit orange foods to a maximum 1 serving from each food category daily.

Notes: Nutritional amounts are based on average values for the variety of foods within each food category.

Dietary prescription is subject to the discretion of the health practitioner.

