[figure not shown]

Pilot Study: Investigating a Novel Supplement-based Therapy for the Treatment of Small Intestinal Bacterial Overgrowth

[name].
Senior Director, Scientific Affairs at Atrium Innovations

Version #2
May 3, 2017

Study Synopsis

The aim of this pilot study is to determine the efficacy of a supplement protocol combined with a low FODMAP diet for the treatment of small intestinal bacterial overgrowth (SIBO). The study is designed as a prospective, open label investigation, with an estimated sample size of 10 patients.

Patients diagnosed with SIBO by [name] at Good Medicine Clinic (Oxford, Ohio) will be offered the opportunity to enroll in this study, if they satisfy the inclusion and exclusion criteria upon initial diagnosis. No control group will be assigned.

The diagnosis of SIBO will be determined via assessment of clinical symptoms and the results of a lactulose breath test. This diagnosis procedure is, currently, the standard-of-care. After administration of the supplement therapy and adherence to a low FODMAP diet (8 weeks), the lactulose breath test will be repeated and symptoms re-assessed by [name].

The post-treatment lactulose breath test and all supplements in the protocol will be provided free-of-charge to enrolled patients. In addition, enrolled patients will not be billed for the mid-treatment office visit. Patient and/or patient insurance will be responsible for all other expenses, including but not limited to the initial breath test, all other office visits and travel.

Background

Small intestinal bacterial overgrowth (SIBO) is a category of gastrointestinal infection, characterized by an increased concentration ($>100,000$ CFU/mL proximal jejunal fluid) of bacteria in the small intestine.¹ Symptoms of SIBO commonly afflict the gastrointestinal tract and include but are not limited to: abdominal pain, discomfort, bloating, cramping, flatulence, diarrhea, constipation, eructation, and low serum B12.^{3,4}

SIBO is believed to be severely under diagnosed and is associated with numerous comorbid conditions including irritable bowel syndrome, diabetes mellitus and hypothyroidism.^{4,5} Small-bowel aspiration (SBA) or breath tests are used to aid in the diagnosis of SIBO. Due to the cost and invasive nature of SBA, glucose or lactulose breath tests are more commonly performed.

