Visit -1 [name] will assess patient history and symptoms, at his facility in Oxford, Ohio. If suggestive of SIBO, a lactulose breath test will be prescribed. Additional testing may be performed, at the discretion of [name], to aid in the initial diagnosis of the patient.

Visit 0 [name] will assess the results of the breath test and confirm or deny the diagnosis of SIBO. Treatment options for SIBO will be discussed, and the patient will be made aware of this investigation as a theoretical treatment option. Patient eligibility will be determined by [name] who will complete the Patient Eligibility Checklist (Appendix A) for each patient. All female patients will be asked to complete a urine pregnancy test to confirm pregnancy status. Eligible patients will be asked to review

and sign the Informed Consent document. [name] (Medical Assistant at Good Medicine) will be available to discuss patient consent and confidentiality. Enrolled patients will be asked to complete a baseline Medical Symptom Questionnaire (Appendix B). Afterwards, [name] will review the supplement therapy (Supplement Overview - Appendix C) and low FODMAP diet (Low FODMAP Handout - Appendix D). Patients will then be provided with all supplements necessary to complete the investigation. Patients will be asked to discontinue all other supplements during the study. However, no wash out period is required. Prescription medications, over-the-counter medications and/or supplements deemed medically necessary by the patient's primary care physician and/or [name] may be continued, if there are no known contraindications.

Visit 1 Visit 1 will occur approximately 4 weeks after the patient begins the supplement protocol. Patients will be asked to report their compliancy with the supplement protocol and low FODMAP diet and describe adverse effects. Patients will also be asked to complete the Medical Symptom Questionnaire. Patients will be provided with the second lactulose breath test kit and instructed to perform the test within 2 weeks of completing the supplement therapy.

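### Does one 180-capsule bottle of digestive enzymes contradict as-needed use of up to 6 a day over 8 weeks?

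*Protocol*

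**What the plan says.** The Product Overview in Appendix C has one row per product, with bottle size, daily use, duration and number of bottles. For Digestive Enzymes Ultra with Betaine HCl the entries are 180 capsules, "As needed (up to 6" capsules a day, a duration described only as long term, and one bottle. A footnote to the bottle column reads "The number of capsules purchased may exceed the amount required by this protocol, due to limited bottle sizes". A second footnote says "Digestive Enzymes Ultra with Betaine HCl may be replaced with Digestive Enzymes Ultra, if patient responds poorly to Betaine HCl".

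The weekly table in the same appendix prints "1-2 capsules or as needed before meal" at breakfast, lunch and dinner in every block from Week 1 to Weeks 7 and 8.

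Two statements in the body of the protocol concern supply. Under Visit 0 in Study Procedures: "Patients will then be provided with all supplements necessary to complete the investigation". In the Study Synopsis: "all supplements in the protocol will be provided free-of-charge to enrolled patients". At Visit 1, about 4 weeks in, patients report compliance and receive the second breath test kit. No later supply of supplements is mentioned there or elsewhere.

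**The concern.** A reader who checks the bottle column finds that every other product is supplied in at least the amount its row calls for. A.C. Formula II even gets a second bottle because one would not be enough. Only the enzyme row can fall below the use the same page permits, and the first footnote speaks of surplus, never of shortage. Set beside the Visit 0 commitment, this looks like a supply figure that does not honour a stated promise.

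If it were a real shortfall, patients at the upper end of permitted use would run out of one component before week 8. The regimen they completed would then differ from the one described, for a reason unrelated to tolerance or choice. The breath test that follows, which patients are "instructed to perform the test within 2 weeks of completing the supplement therapy", would come after an incomplete course of that component. The product-swap footnote adds a smaller loose end, since it gives no quantity for the replacement.

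**Working it through.** **Inputs, all from Appendix C:** 180 capsules per bottle; one bottle listed; ceiling of 6 a day; 1 to 2 capsules at each of 3 meals, or as needed; 8 weeks = 56 days. The 56 days come from the weekly table, because the overview gives no number of days for this product.

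**Step 1. Reproduce the plan's other bottle counts.** Amount needed = daily use × days; amount supplied = bottle size × bottles.

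| Product | Needed | Supplied |
|---|---|---|
| Liver-G.I. Detox | 2 × 30 = 60 | 60 |
| L-Glutamine (scoops) | 2 × 35 = 70 | 73 |
| MicroDefense | 1 × 49 = 49 | 90 |
| A.C. Formula II | 4 × 49 = 196 | 2 × 120 = 240 |
| Probiotic-5 | 1 × 49 = 49 | 60 |

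All five listed counts are the smallest number of bottles that covers the stated use.

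**Step 2. Apply the same rule to the enzymes over 56 days, with 180 supplied.**

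| Mean use per day | Needed (use × 56) | 180 − needed | Bottle lasts (180 / use) | Days of the 56 without stock |
|---|---|---|---|---|
| 3 | 168 | 12 over | 60 days | 0 |
| 4 | 224 | 44 short | 45 days | 11 |
| 5 | 280 | 100 short | 36 days | 20 |
| 6 | 336 | 156 short | 30 days | 26 |

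The break-even mean is 180/56 = 3.21 capsules a day. The listed single bottle is therefore reproduced at 1 capsule per meal and is not reproduced at the ceiling.

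**Step 3. Place the break-even in the permitted range.** If as-needed use is read as 0 to 6 a day, 3.21 is 3.21/6 = 54% of the ceiling. If it is read as a strict 3 to 6 a day, 3.21 is (3.21 − 3)/(6 − 3) = 7% of the way up. The text sets no lower limit, so the second reading assumes that no capsule is ever skipped. Under an as-needed rule a skipped capsule offsets an extra one. The protocol gives no expected use, so the share of patients above 3.21 cannot be computed.

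**Step 4. Compare the timing with the visit schedule.** At 6 a day, use by day 28 is 6 × 28 = 168, leaving 180 − 168 = 12 capsules, or 2 days. Visit 1 falls at about that point and asks about compliance, so even the fastest permitted user has a scheduled contact at about the time the bottle runs out.

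**Step 5. Cost of closing the gap in practice.** Two bottles give 360 against 336 at the ceiling, with 24 left over. At an estimated 10 patients that is at most about 10 further bottles.

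**The case for a change.** The strongest case for a change is that a promise to provide everything necessary should hold across all the use the same document allows, and that the only quantity printed does not do so. The weekly table prints 1 to 2 capsules at each of three meals, and most of that 3 to 6 range lies above 3.21. The long-term duration makes one bottle look less adequate. A correction would cost one table cell or one sentence, and supply quantities are not something a protocol leaves to its statistical analysis plan.

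Much of this stands. The figures are correct, no resupply is written down, and a fuller protocol would have said how further enzyme stock or a replacement product reaches the patient.

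The step from there to a contradiction does not stand. The five other rows have a fixed daily amount and a fixed number of days, so a bottle count follows from them. The enzyme row has neither, and no finite count could cover an open-ended duration. Its one bottle is reasonably read as a starting quantity. The Visit 0 and Synopsis statements promise sufficient supply at no charge and name no number of bottles. They conflict with the table only if the site is assumed to hand over exactly one bottle and nothing later, which the protocol does not say.

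The breath test argument is also weak. The test follows completion of the therapy, so having no enzymes left on that day is not in itself a departure from the plan.

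**Conclusion.** No change to the plan is called for. What remains is an unstated supply detail for one optional-use product. It is not an error of arithmetic, since no printed figure is wrong: one bottle covers 56 days up to a mean of 3.21 capsules a day, which includes the low end of the printed schedule (168 of 180).

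Above that mean a single bottle falls short, by up to 156 capsules and 26 days at the ceiling. This matters only if two conditions both hold: mean use exceeds 3.21 a day, and the site supplies nothing further. The protocol gives no figure for the first and does not state the second. Its own supply commitment points the other way, and Visit 1 falls at about the time it would matter most.

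Writing down a resupply step would alter no endpoint, comparison or conclusion in this open-label pilot of about 10 patients. No effect on the pre- and post-treatment comparison has been shown. The site can be expected to fill the gap by honouring what Visit 0 already says. The conclusion assumes 56 days of use and takes no view on how many capsules a patient should take.

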Visit 2 Visit 2 will occur after the results of the post-treatment breath test are available. [name] will interpret the results of the second breath test, and patients will be asked to complete the Medical Symptom Questionnaire, report compliancy with the supplement protocol and low FODMAP diet, and describe any adverse effects. Further treatment options will be discussed if necessary; follow-up treatment will be outside the scope of this investigation.

Risk/Safety Information

This study presents risk in the form of adverse reactions to ingredients in the supplement therapy. Patient risk will be minimized by excluding patients who may respond poorly to the supplement therapy or testing procedures from the study, i.e., by abiding by the aforementioned patient enrollment exclusion criteria.

Monitoring/Reporting

Patients may report adverse events to Good Medicine during scheduled office visits or by phone during office hours. If serious or life-threatening side effects arise, patients are instructed to call 911. Possible side effects include but are not limited to: diarrhea, constipation, nausea, vomiting, bloating or headache. When necessary, [name] or [name] will communicate with patients outside the office by phone and record adverse events in the patient's confidential files. Medical guidance will be provided as necessary.

Study Oversight

This study will be terminated if one-half or more of enrolled patients withdraw due to adverse events. [name] and [name] (Senior Director, Scientific Affairs at Atrium Innovations) will monitor, determine the need for and facilitate the termination of the study. Direct access to study related data will be made available for monitoring, auditing, IRB review and regulatory inspection.

Data Management

Lactulose breath test scores and completed Medical Symptom Questionnaire will be compared pre- and post-treatment to determine the efficacy of the supplement therapy. The significance of the change in breath test scores will be determined if the final sample size permits such analysis.

IRB Review/Ethics/Informed Consent

This study will be conducted in accordance with the ethical principles that have their origin in the Declaration of Helsinki and that are consistent with Good Clinical Practice and applicable regulatory requirements.

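### Appendix C lists one 180-capsule bottle of the enzyme product, but its own 8-week schedule allows up to 336 capsules, so the listed supply covers only about 3.2 a day (minor).

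*Protocol*

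**What the plan says.** Appendix C (Product Overview) gives the enzyme product 180 capsules per bottle, a daily amount of "As needed (up to 6"), a duration of 'Long term', and one bottle. The other five products each have a fixed daily amount and a duration in days. A footnote to the bottle column explains that bottle sizes can leave a patient with more capsules than the regimen uses. It says nothing about a shortfall.

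The dosing grid in the same appendix lists the enzyme product at breakfast, lunch and dinner in every block of weeks 1 to 8, each time as "1-2 capsules or as needed before meal". On length, Appendix C states: "This protocol is designed to take 8 weeks". Study Procedures gives the same 8 weeks.

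On supply, the Study Synopsis says "all supplements in the protocol will be provided free-of-charge to enrolled patients", and Visit 0 says "Patients will then be provided with all supplements necessary to complete the investigation". On timing, patients at Visit 1 receive the second breath test kit and are "instructed to perform the test within 2 weeks of completing the supplement therapy". At Visit 1 and again at Visit 2, patients report how well they kept to the supplements and the diet.

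**The concern.** The table fixes how much of each product a patient is given, and the grid fixes how much the patient may take. For five products the two agree. For the enzyme product they agree only near the bottom of the printed dose range. If one bottle is dispensed as listed, a patient who takes two capsules at some or all meals, as the grid allows, will run out before week 8. That patient then receives less of one of the six products than the regimen permits, for a reason unrelated to need or tolerance.

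A second, smaller matter sits in the same row. A duration of 'Long term' beside a grid that stops at week 8 does not say whether the enzyme may be taken between week 8 and the second breath test. One patient could stop and another continue, and both could point to Appendix C.

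**Working it through.** **Inputs, all from the Protocol.** Capsules per bottle, daily amounts, durations and bottle counts come from the Appendix C product table. The per-meal dose and the weeks come from the Appendix C grid. The course is 8 weeks = 56 days.

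**Step 1: does the table's rule work for the other products?** Need = daily amount × days; supply = bottles × servings per bottle.

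| Product | Need | Supply | Covered |
|---|---|---|---|
| Liver-G.I. Detox | 2 × 30 = 60 | 60 | yes |
| L-Glutamine | 2 × 35 = 70 | 73 | yes |
| MicroDefense | 1 × 49 = 49 | 90 | yes |
| A.C. Formula II | 4 × 49 = 196 | 2 × 120 = 240 | yes |
| Probiotic-5 | 1 × 49 = 49 | 60 | yes |

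The rule reproduces all five bottle counts. A.C. Formula II has two bottles because one (120) would fall short of 196. The count for Detox is exact, and it agrees with the grid entry "Liver-G.I. Detox (finish 2 days into week 5"), since 4 × 7 + 2 = 30 days.

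**Step 2: the enzyme row.** One to two capsules at three meals is 3 to 6 a day, and the upper end equals the table's stated maximum. Supply is 1 × 180 = 180.

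| Capsules a day | Need over 56 days | Bottle lasts (180 ÷ dose) | Days uncovered | Shortfall |
|---|---|---|---|---|
| 3 | 168 | 60 days | 0 | 0 |
| 4 | 224 | 45 days | 11 | 44 |
| 5 | 280 | 36 days | 20 | 100 |
| 6 | 336 | 30 days | 26 | 156 |

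The break-even dose is 180 ÷ 56 = 3.2 a day. One bottle is therefore right at one capsule per meal and too few at 4, 5 or 6 a day. Because use is as needed, 336 is a ceiling and 168 is not a floor.

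**Step 3: could the gap be seen in time?** Visit 1 falls at about day 28.

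| Capsules a day | Left at day 28 | Needed for days 29–56 |
|---|---|---|
| 3 | 180 − 84 = 96 | 84 |
| 4 | 180 − 112 = 68 | 112 |
| 5 | 180 − 140 = 40 | 140 |
| 6 | 180 − 168 = 12 | 168 |

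Even at 6 a day the bottle is not yet empty at day 28, so a shortage could be noticed and made good at Visit 1.

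**Step 4: two bottles.** Supply is 2 × 180 = 360, which covers 336; 360 ÷ 56 = 6.4 a day.

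**Step 5: the duration cell.** If therapy ends on day 56, the breath test falls on days 57–70. By design every patient is then 27–40 days past Detox (ends day 30), 15–28 days past L-Glutamine (ends day 42) and 1–14 days past the three products that end with week 8. Only for the enzyme does the table leave open whether it is still being taken.

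**The case against.** The best defence is that an as-needed product has no fixed requirement, so one starting bottle is a reasonable listing. It covers one capsule per meal for the whole course (168 of 180). The document gives no expected use, so nothing shows that any of about ten patients would run short. The synopsis and Visit 0 also commit to supplying what patients need, and nothing makes the bottle count a cap. Resupply is not barred, and by Step 3 a shortage is visible at Visit 1.

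Much of this stands, and it is why the point is minor. It does not remove the mismatch. Four a day is well inside the printed range and already exceeds one bottle. The footnote covers surplus only, Visit 0 describes supplements being handed out then for the whole study, and no resupply step is written.

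On duration, a reader might infer that 'Long term' leaves the therapy without an end and so the second breath test without a date. The document does not support that. The synopsis, Study Procedures and Appendix C all give 8 weeks, and the grid stops at week 8, so completion of therapy has a date. 'Long term' may simply mean optional use after the study. A reader might also infer that differences in enzyme use would go unrecorded. That is too strong, because at Visit 2 patients "report compliancy with the supplement protocol and low FODMAP diet". Only a specific last-capsule date is not asked for.

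**Conclusion.** The supply point holds. The enzyme row is the only one whose listed bottles do not cover its own printed daily maximum: 180 capsules against a permitted 168 to 336, with a break-even of about 3.2 a day. Without resupply, patients at 4, 5 or 6 a day would lack the product for the last 11, 20 or 26 days. This assumes that one bottle is dispensed as listed and that the dose is constant. How many patients would use that much is not stated.

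On duration, what remains is one unclear cell: it does not say whether enzymes may continue after week 8, into the breath test window.

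Severity is minor. It may be tempting to read uneven enzyme use as a bias in the pre/post comparison, but the document gives no basis for the size or direction of any effect on breath test or symptom scores. Nor is being off a product before the test a fault in itself, since Step 5 shows that the schedule takes every patient off two others weeks earlier.

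**What to change.** In the Appendix C product table, change the enzyme row to two bottles (360 capsules). The dose range and the option to switch to the version without Betaine HCl stay as they are.

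The cost is one extra bottle per patient, or 20 instead of 10 for ten patients. Some of it goes unused: 360 − 336 = 24 capsules at 6 a day, 80 at 5, 136 at 4, 192 at 3, and more at lower use.

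For the duration cell, at most record at Visit 2 whether the enzyme was still being taken after week 8 and, if not, the date of the last capsule. This adds one item per patient to the compliance report. Imposing a stop on day 56 would be a design choice for the sponsor and is not needed to correct an error. If the sponsor instead wants enzymes supplied through day 70, two bottles cover 5 a day (350) but not 6 (420).
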